8.5. Blinding and code-breaking

This study does not involve blinding. However, to incorporate a degree of impartiality, assessments will be carried out by a research assistant, not the therapist.

8.6. Assessments

All participants will undertake the baseline assessment in the same week, following a concurrent randomised multiple-baseline study design. Participants will undertake three assessment visits with the research assistant (these are referred to in SCED terminology as ‘standard’ assessments), and frequent ratings of the two primary constructs between assessments, throughout the course of the study (these are referred to as ‘target’ assessments)³¹. All assessments will use a study ID in place of identifying information.

9.6.1 ‘Standard’ Assessments

The baseline, post-intervention, and follow-up assessments will each last approximately 50 minutes. The assessment will be conducted at an NHS or University of Birmingham building, or the participant’s home, based on participant preference. The assessment will be conducted on an individual basis, with only the participant and researcher present. Assessments can be conducted remotely (for example using telephone, online, or postal versions) if necessary. Online assessments may be in the form of either: the participant annotating an electronic (Word document) version of the measures; the RA annotating a hardcopy or electronic copy of the measures whilst on a call with the participant; or via Qualtrics. Self-addressed stamped envelopes will be provided for participants returning measures by post, in the case that it is not practicable for the RA to collect these in person to ensure safe receipt.

All assessments in the study are self-report measures; except for the recording of the participant’s clinical diagnosis and current prescribed medication, which will be extracted from their clinical records at each assessment point. Permission to access clinical records for this purpose will be obtained during the informed consent process.

The self-report outcomes collected at all three standard assessments are:

1. ‘Felt sense of anomaly’ (FSA)-type dissociative symptoms:

- [name] Felt Sense of Anomaly scale – revised (ČEFSA-14; [name] et al., *in prep.* – based on the original ČEFSA²¹)
- Visual analogue scale (VAS) rating 0-100 for FSA-dissociation.

2. Possible mechanisms of FSA-type dissociation:

- Cognitive Appraisals of Dissociation in Psychosis scale (CAD-P²);
- Perseverative Thinking Questionnaire (PTQ⁵);
- Affect Intolerance Scale (AIS¹);
- Online Alexithymia Scale (amended) (OAS⁴);
- General Self Efficacy scale (GSE³);
- Responses to Dissociation scale (RTD⁴).
- VAS rating (0-100) for the study-specific mechanism of interest (i.e., cognitive appraisals [study 1]; perseverative thinking [study 2]; affect intolerance [study 3]).

3. Self-harm:

- One item asking the frequency of recent self-harming behaviours. A full validated measure of self-harm and suicidality is not included as this study is not powered to establish clinical effect, but nevertheless, this rough indicator will provide helpful insight for future studies as it has been suggested that self-harm may also act as a mechanism or trigger for dissociative experiences⁸.

Additionally, at the baseline assessment (only), basic demographics (age, gender, ethnicity) will be collected, and a brief summary of the participant's previous experience receiving psychological therapy.

9.6.2 'Target' Assessments

Between standard assessments, participants will be asked to complete two visual analogue scales (VAS) either daily (during the baseline (A₁) phase), or every other day (during the intervention (B₁) and follow-up (A₂) phases). These will ask the participant to rate from 0 to 100: 1) the severity of the distress caused by dissociation since the last rating, and 2) how much they have been bothered by the study-specific psychological factor (i.e., cognitive appraisals [study 1]; perseverative thinking [study 2]; affect intolerance [study 3]) since the last rating.

To help participants remember to complete these measures, and to reduce participant burden, participants will decide with the research assistant the most convenient way for them to complete the scales (e.g. via telephone call, text message, completion of an online survey link sent via email or text, or taking home a supply of paper copies), and how they would like the researcher to remind them to complete these (e.g., a daily text, automated emails, or a call once a week). Responses received via text will be transferred and stored on UoB servers as per UoB IT guidance.

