5. OBJECTIVES AND OUTCOME MEASURES

The primary objective is to determine whether there is sufficient reason to believe that each psychological intervention targets (reduces) the psychological maintenance mechanism (factor) of interest in that study to justify running a larger study. For Study 1 the mechanism of interest will be negative cognitive appraisals of the dissociative experiences; in Study 2, perseverative negative thinking (rumination); and in Study 3, affect intolerance (aversion to the experience of one's own emotions). Therefore, the key outcomes will be measures of these three psychological factors: cognitive appraisals of dissociation, perseverative thinking, and affect intolerance.

Of relevance to future treatment development for dissociation, the secondary objective of this project is to gain a preliminary indication of the effect targeting the above mechanisms has on levels of dissociation – i.e. whether this relationship is causal. There will not be adequate statistical power in these studies to definitively answer this research question. However, data from this study may aid future research by providing initial estimates for sample size calculations.

Since we are interested in further testing and developing the techniques in this project (if this is justified by the data), we will also ask participants for qualitative feedback about their experiences of the intervention and research processes at the end of their participation, and use the experience of running this study to inform which patient-facing logs, worksheets, and diaries may be most useful in developing a future intervention.

These objectives and outcomes are summarised below:

	Objectives	Outcome Measures	Timepoint(s)
Primary	To determine whether the psychological intervention is likely to reduce the psychological maintenance mechanism (factor) of interest (i.e. cognitive appraisals [study 1]; perseverative thinking [study 2]; affect intolerance [study 3]).	Study 1: CAD-P Study 2: PTQ Study 3: AIS	VAS rating: daily (throughout baseline and intervention window), or every other day (throughout follow-up window). Full measure rating: baseline, post-intervention, one month follow-up.
Secondary	To gain a preliminary indication of whether the relationship between the proposed psychological factor (cognitive appraisals; perseverative thinking; affect intolerance) and 'felt sense of anomaly'-type dissociation may be causal.	As above + ČEFSA-14	As above.

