6. STUDY DESIGN

This project consists of three randomised multiple baseline design (MBD) single case experimental design studies, with an A₁B₁A₂ structure (Appendix A).

Each study will have four participants. After completing a baseline assessment, each will be randomised to a different length of baseline (phase A₁) duration (either 1, 2, 3 or 4 weeks). During A₁, participants will rate the target maintenance mechanism (factor) and their level of dissociation daily (see Section 9.6, *Assessments*).

The treatment window (phase B₁) for each participant in all studies will be five weeks. In this time, participants will have four 1:1 one-hour long psychological therapy sessions with a qualified clinical psychologist who will deliver the study intervention (see Section 10, *Study Interventions*). Between-session tasks will be set as part of this intervention, to be completed by the participant alone, or with telephone or additional in-person support from the research team. Participants will continue to rate the maintenance mechanism factor and their dissociation every other day. At the end of the intervention window (phase B₁), participants will repeat the baseline assessment measures in a ‘post-intervention’ assessment.

The follow-up phase – phase A₂ – will last for one month following the closure of the intervention window (phase B₁). In this phase, participants will continue to make ratings of the maintenance mechanism factor and their dissociation every other day. At the end of phase A₂, participants will complete the baseline assessment measures again in a ‘follow-up’ assessment, and will be offered the chance to provide unstructured qualitative feedback about the research processes and intervention.

This project will be registered with ClinicalTrials.gov.

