9.1. Study 1 – Negative Cognitive Appraisals of Dissociative Experiences

The key therapeutic technique delivered in this intervention will be cognitive restructuring, drawn from classical cognitive-behavioural therapy (e.g.³⁴).

Participants will be supported to understand what cognitive appraisals are, learn to notice and record these using a cognitive appraisals log/diary, and then supported to use an extended log/diary to challenge and adjust any negative assumptions contained within these. The aim is for participants to become more aware of the automatic appraisals they are making of their dissociative experiences and replace these with more balanced judgements.

There is extensive evidence for the use of this technique across the full range of mental health presentations, particularly in depression and anxiety, but also in a dissociative diagnosis: depersonalisation disorder³⁵.

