9.3. Study 3 – Affect (Emotion) Intolerance

The key therapeutic techniques delivered in this study will be drawn from CBT and dialectical behavioural therapy (DBT).

Participants will be supported to explore their own beliefs about emotions (CBT) and learn why affect is necessary and adaptive for daily life (DBT). They will work with the therapist to identify their individual triggers for affect intolerance (CBT/DBT) and respond to these in the most relevant way,

including: learning and practicing DBT coping strategies; carrying out behaviour experiments to test their assumptions/beliefs (CBT); or carrying out cognitive restructuring to balance beliefs/appraisals (using the same techniques as in Section 10.1, *Study 1*; CBT).

These techniques have been used effectively in the treatment of emotion dysregulation and affect intolerance³⁹. They are therefore anticipated to have a similar effect in the context of dissociation.

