11.1. Statistical Analysis

Given the design and sample size, analysis will be descriptive in nature and no hypothesis testing will be carried out. The three studies will be analysed separately according to the following analysis plan.

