16.4. Other Ethical Considerations

We anticipate few ethical concerns for patients entering this study. The study will be conducted by a CI who is a qualified clinical psychologist with extensive experience of clinical trials, and who has

appropriate training regarding the management of any risk or safeguarding issues that may arise during the course of the study. There is a risk that safeguarding concerns are raised (e.g. identification of risk of self-harm etc.). These will be reported as soon as possible to the direct care team, and the participant supported appropriately within the boundaries of the trial (e.g. signposted to Samaritans, reminded of existing risk-management plan, etc.).” Participation in the study does not change existing treatment receipt, so there is no disadvantage in taking part. Participants will be free to discontinue the study at any point, without needing to give an explanation.

The main potential problem is the burden of assessments (three visits and daily/alternate-day reporting for two key items); however, most trials with similar patient groups show a modest symptom benefit of entering the control condition in a therapy trial, most likely due to the additional monitoring and sensitive manner of the research assessors (e.g.⁴³). We offer payment for participants’ time and flexibility in the assessments, such as providing breaks, or arranging for these to take place at a location of participants’ choice – including online. The study questionnaires ask participants about their mental health, which may be considered a sensitive topic. However, these are issues participants are already managing outside of the study, and they will have experience of talking about them as part of the treatment they are receiving from NHS services. Research assistants are trained to ask questions sensitively and participants are informed that they do not have to answer any questions if they do not want to.

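### The repeated dissociation rating is described as level in one section and as distress in another, and it is the only dissociation series the phase and Tau-U analysis can use

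*Combined protocol and SAP*

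**What the plan says.** The secondary objective in Section 5 is to gain a "preliminary indication of the effect targeting the above mechanisms has on levels of dissociation". Section 6 describes the repeated rating in matching terms: in the baseline phase, "participants will rate the target maintenance mechanism (factor) and their level of dissociation daily".

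Section 9.6.2 (Target Assessments, printed under 8.6) gives the content of the two between-visit scales. Item 1, scored 0 to 100, is "the severity of the distress caused by dissociation since the last rating". Item 2 asks how bothered the participant has been by the factor that the study targets. The lay summary, Section 9.6.1 and Appendix B refer to a dissociation score or scale and do not mention distress.

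ČEFSA-14 is the named secondary measure and is taken at the baseline, post-intervention and follow-up visits. Section 12.1.1 (under 11.1) judges change from within- and between-phase patterns and calculates Tau-U if those patterns indicate an effect. Section 11.6 leaves out any phase with under five points.

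**The concern.** Level and distress are different quantities, and the protocol itself treats them so. Section 4 defines dissociation as feelings of unreality, unfamiliarity or disconnection, and then says separately that such experiences can be distressing. Its cognitive model also separates the experience from the threatening interpretation placed on it.

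The difference matters most in Study 1. That therapy aims to make participants more aware of the "automatic appraisals they are making of their dissociative experiences and replace these with more balanced judgements". If it works as intended, a person could have the same experiences as before and mind them less. Item 1, read as distress, would fall. Item 2, worded as bother, could fall with it for the same reason. Two series falling together is the pattern that would be taken as a sign that the factor acts on dissociation, yet lower distress alone could produce it.

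At stake is the reading of the secondary result. Section 5 also says the data may supply initial estimates for later sample-size work. If the Tau-U from this series were used for that, it would be an estimate for distress.

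**Working it through.** **1. The descriptions side by side**

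| Place | What is rated |
|---|---|
| Section 5, secondary objective | level of dissociation |
| Section 6, repeated rating | level of dissociation |
| Section 9.6.2, item 1 | distress caused by dissociation |
| Lay summary, Section 9.6.1, Appendix B | dissociation; distress not mentioned |

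Sections 6 and 9.6.2 describe one rating in two ways. Section 9.6.2 is the more specific, but neither reproduces the form.

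**2. Scheduled ratings on the repeated scale, if all are completed**

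- Baseline phase A1, daily for 1, 2, 3 or 4 weeks: 7 × weeks = 7, 14, 21 or 28.
- Intervention phase B1, 35 days on alternate days: 35 / 2, so 17 or 18.
- Follow-up phase A2, one month (28 to 31 days) on alternate days: 14 to 16.
- Total: 7 + 17 + 14 = 38, up to 28 + 18 + 16 = 62.

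The synopsis and the Section 5 table have B1 rated daily, whereas Sections 6, 8 and 9.6.2 and Appendix B have alternate days. With B1 daily the total is 7 + 35 + 14 = 56, up to 28 + 35 + 16 = 79. On either schedule every phase exceeds five points.

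**3. Can any other dissociation measure form a phase series?**

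- ČEFSA-14: three visits, so at most 3 points in any phase however visits are assigned to phases, and 1 per phase on the natural assignment. This is below 5.
- Screening ČEFSA-14: Section 8.2 has these forms destroyed. Counting it would still give at most 3 + 1 = 4.
- Visit scale for dissociation: three visits, so again at most 3.

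The synopsis sets ČEFSA-14 against the daily timepoints, which could suggest a daily questionnaire. The Section 5 table, Section 9.6.1 and Appendix B place the full measure at the three visits.

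For A1 against B1, the repeated scale offers 7 × 17 = 119 to 28 × 18 = 504 pairwise comparisons per participant on the alternate-day schedule. ČEFSA-14 offers 1 × 1 = 1.

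**4. What follows.** If Section 9.6.2 is right, the dissociation phase analysis and Tau-U are an analysis of distress, and level is seen only through three ČEFSA-14 scores. If Section 6 is right, the analysis matches the objective and only Section 9.6.2 is wrong.

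**The case against.** The strongest reply is that this is a contradiction in drafting, not a demonstrated design flaw. Section 6 says level, the other mentions are neutral, and the form is not shown. That stands: any effect on interpretation depends on the form following Section 9.6.2.

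A second reply is that level is measured, by ČEFSA-14, and nothing bars it from the overall judgement. This also stands. A reader might infer that the plan has no measure of the level of dissociation, and that would be wrong. What ČEFSA-14 cannot supply is a phase series.

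A third is that Section 5 asks only for a preliminary indication and disclaims a definitive answer, and that Tau-U is conditional on the patterns suggesting an effect. Both are true, and they limit the consequence without removing it.

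A reader might extend the point to Study 3, because its therapy may include "carrying out cognitive restructuring to balance beliefs/appraisals (using the same techniques as in Section 10.1". The documents do not carry that far. In Study 3 the restructuring sits within work on beliefs about emotions and triggers for affect intolerance, so a shared technique is not a shared target. Only Study 1 works directly on appraisals of dissociation.

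A reader might also conclude that item 2, and hence the primary series, is unsound because it too is framed as bother. Its wording is relevant here only because it lets both Study 1 series share a distress component. Whether bother is an adequate rating of each mechanism is a separate question, not settled by this point.

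**Conclusion.** The point holds as an inconsistency with a specific consequence. Sections 5 and 6 concern the level of dissociation, and Section 9.6.2 has participants rate the distress it causes. The repeated scale (38 to 62 ratings, or 56 to 79 with daily B1, assuming full completion) is the only dissociation series that can enter the phase and Tau-U analysis. If Section 9.6.2 is followed, a fall in that series cannot by itself show that dissociation fell, and in Study 1 both series could fall through reduced distress alone.

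The documents do not say how much of any fall would be distress alone; it could be anything from none to all. They do not show that the wrong construct is being collected, since the form is unseen. No sample-size figure is affected. The effect is confined to how the secondary result is read and labelled.

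**What to change.** Check the rating form, then reconcile Sections 5, 6, 9.6.1 and 9.6.2 with it.

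- **If the form asks about level:** correct Section 9.6.2. Nothing else changes.
- **If it asks about distress:** decide study by study, which fits the plan, since "The three studies will be analysed separately according to the following analysis plan".
  - *Ratings not begun:* reword item 1 to rate the level (strength or frequency) of felt-sense-of-anomaly experiences since the previous rating, and use the same wording at the visits.
  - *Ratings under way:* leave the item alone. Report its phase analysis and Tau-U as distress caused by dissociation, present the ČEFSA-14 scores beside it descriptively as the measure of level, and claim no effect on level from the repeated scale alone. State this in Section 12.1.1 before analysis.

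Costs: rewording adds no answers for participants, but it gives up the distress series, leaves item 2 worded as bother, and may make item 1 differ between studies. It also needs an amendment, with sponsor review and further approval if substantial (Section 16.3).

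Time may have closed that route. The synopsis ends the study on 5 March 2024 and gives 12 to 15 weeks per participant. Counting back 15 and 12 weeks gives latest starts of about 21 November to 12 December 2023, and version 3.0 is dated 4 December 2023. Whether ratings had begun is not stated, so on the planned dates only the labelling route may remain. That route adds nothing for participants; its price is that the phase analysis then speaks to distress, with three ČEFSA-14 scores as the only view of level.

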9.6.3 Qualitative Feedback

At the end of the follow-up assessment (only), participants will be given the opportunity to provide qualitative feedback regarding the study procedures and therapy. This is voluntary. If a participant does choose to give feedback, they will be given the option of providing written or audio-recorded feedback (consent for audio recording capture, storage, and transcription will be covered in the ICF for the study) in the follow-up assessment appointment.

Additionally, all participants will be given a link to an anonymous online 'comments box' (online survey text box on Qualtrics) in case they wish to give feedback after the appointment, or do not feel comfortable giving feedback to the research assistant directly.

The feedback will take an unstructured form, with no topic guide or interview schedule – except that participants will be prompted to provide feedback on 'how you found both the study process, and how you found the therapy', and that 'we are interested in negative feedback as well as positive, so that we can learn how to improve the experience for future participants'.

If feedback is given verbally, it will be audio-recorded and transcribed verbatim. All feedback will be analysed using Thematic Analysis³². Quality guidelines³³ will be followed, including credibility checks and reflexive practice. This approach has been used before by the CI with a similar participant group⁶.

8.7. Early Discontinuation/Withdrawal of Participants

During the course of the study, a participant may choose to withdraw early from the study at any time. This may happen for several reasons, including but not limited to:

- The occurrence of what the participant perceives as an intolerable AE.

- Inability to comply with study procedures
- Participant decision

Participants may choose to stop treatment and/or study assessments but may remain on study follow-up. Participants may also withdraw their consent, meaning that they wish to withdraw from the study completely. Withdrawal from the study or intervention will not affect their usual care.

According to the design of the study, participants may have the following two options for withdrawal;

- 1) Participants may withdraw from active follow-up and further communication but permit data obtained up until the point of withdrawal to be retained for use in the study analysis. No further data would be collected after withdrawal.
- 2) Participants can withdraw completely from the study and withdraw the data collected up until the point of withdrawal. The data already collected would not be used in the final study analysis, unless analysis has already begun/been completed.

In addition, the Investigator may discontinue a participant from the intervention at any time if the Investigator considers it necessary for any reason including:

- Ineligibility (either arising during the study or retrospectively having been overlooked at screening);
- An adverse event which requires discontinuation of the intervention;
- Clinical decision.

If the participant is withdrawn due to an adverse event, the Investigator will arrange for follow-up visits or telephone calls until the adverse event has resolved or stabilised.

The reason for withdrawal will be recorded in the CRF.

